LIST OF FIGURES

Figure 1 – Trial Flow Diagram.....	16
Figure 2 – Gantt Chart of research timetable	45

TRIAL SUMMARY

Full Title	Remote multicomponent rehabilitation intervention in survivors of critical illness post hospital discharge: a randomised controlled assessor-blind clinical and cost effectiveness trial with internal pilot.
Short title	Remote Rehabilitation After Intensive Care (iRehab)
Duration of Trial	1 st January 2022 – 31 December 2024 (36 months)
Clinical Phase	Phase III
Trial Design	Pragmatic, randomised (allocation ratio 1: 1.17), controlled, assessor blind, multi-centre trial with internal pilot and embedded process evaluation.
Research question:	What is the clinical and cost effectiveness of a remote multicomponent rehabilitation intervention compared to standard care in survivors of critical illness following discharge from hospital after an Intensive Care Unit admission (ICU)
Trial Participants	Adults within 12 weeks of hospital discharge after treatment of a critical illness requiring ICU care and mechanical ventilation for ≥ 48 hours
Planned sample size	428 participants (197 control: 231 intervention) from at least 30 UK sites
Intervention	Six-week remote multi-component, individualised, rehabilitation intervention incorporating: weekly symptom management; targeted exercise; psychological support; and peer support and Information.
Control	Standard care offered at each site
Outcomes	
Measured pre-randomisation, eight weeks, six months post-randomisation
 
Primary: Health-related Quality of Life: EQ-5D-5L at eight weeks
 
Secondary: Physical Function: 30 second sit to stand test Illness Perception: Brief Illness perception questionnaire (BIPQ) Fatigue: Functional Assessment of Chronic Illness Therapy-Fatigue (FACIT-F) scale Anxiety and Depression: Hospital Anxiety and Depression Scale (HADS) Healthcare and social care utilisation Safety: Serious Adverse events Acceptability and Process Evaluation: Theoretical Framework of Acceptability Questionnaire

Follow-up	Remote follow up at eight weeks and six months (26 weeks)

Process evaluation	Qualitative interviews with up to 40 participants from intervention and standard care arms, and up to 30 health care professionals (intervention team members, trial management group members, CTU staff, NHS staff involved in the trial and/or rehabilitation service delivery). Acceptability of rehabilitation or treatments that participants received explored using the Theoretical Framework of Acceptability Questionnaire (TFAQ).
--------------------	---

LIST OF ABBREVIATIONS/GLOSSARY

Abbreviation	Explanation
AE	Adverse Event
CACE	Complier Average Causal Effect
CI	Chief Investigator
CONSORT	Consolidated Standards of Reporting Trials
CRF	Case Report Form
CTU	Clinical Trials Unit
DMC	Data Monitoring Committee
eCRF	Electronic Case Report Form
EQ-5D-5L	European Quality of Life – 5 Dimensions
FACIT-F	Functional Assessment of Chronic Illness Therapy – Fatigue
GCP	Good Clinical Practice
GDPR	General Data Protection Regulation
GP	General Practitioner
HADS	Hospital Anxiety and Depression Scale
HRQOL	Health Related Quality of Life
HSC	Health and Social Care
HSCT	Health and Social Care Trust
HTA	Health Technology Assessment
ICF	Informed Consent Form
ICU	Intensive Care Unit
IRAS	Integrated Research Application System
ISO	International Organisation for Standardisation
ISRCTN	International Standard Randomised Controlled Trial Number
LTFU	Lost to Follow-up
MRC	Medical Research Council
NICE	National Institute Clinical Excellence

NIHR	National Institute for Health and Care Research
NHS	National Health Service
ORCHA	Organisation for Review of Care and Health Apps
PAG	Patient Advisory Group
PI	Principal Investigator
PIS	Patient Information Sheet
PPI	Patient & Public Involvement
QA	Quality Assurance
QALY	Quality of Life Years
QOL	Quality of Life
RCT	Randomised Controlled Trial
REC	Research Ethics Committee
R&D	Research and Development
SAE	Serious Adverse Event
SF-36	Short Form 36 Health Survey Questionnaire
SOP	Standard Operating Procedure
TFAQ	Theoretical Framework of Acceptability Questionnaire
TIDieR	Template for Intervention Description and Replication
TMG	Trial Management Group
TSC	Trial Steering Committee
VAS	Visual Analogue Scale
WCTU	Warwick Clinical Trials Unit

1. BACKGROUND

1.1 Epidemiology and burden of the condition

The UK Intensive Care National Audit and Research Centre, described approximately 172,000 admissions to critical care units in England, Wales, and Northern Ireland, with approximately 129,000 patients surviving critical illness discharged from acute hospitals over one year (April 2019 to March 2020) (1). The consequences of critical illness are substantial and multifactorial, and often encompass physical deconditioning, respiratory and swallowing problems, reduced activities of daily living, cognitive and mental health impairments, fatigue, and declines in health-related quality of life (HRQoL) (2-8). In the UK, one in four people recovering from critical illness experience an unplanned hospital readmission within 90 days of discharge, substantially higher rates of readmission than hospitalised patients without an ICU stay (9). At a societal level, nearly half of ICU survivors fail to return to work after 12 months, (10-11) with UK data highlighting the increase in social care support required (11). Therefore there is a need to intervene to improve the long term health of patients discharged home after intensive care. Identifying ways to support people returning home after a stay in ICU has been ranked a key priority for research by patients, their families, and researchers (12).

Guidance has recommended remote rehabilitation as standard of care for critically ill survivors following COVID-19 (13,14). There is no evidence to support the delivery of remote rehabilitation to the broader population of survivors of critical illness, despite its use and anecdotal evidence of acceptability across many disease populations. This trial will provide evidence on whether remote rehabilitation is clinically and cost-effective for survivors following critical illness post-ICU care. This trial will provide high quality evidence regarding the effectiveness of remote rehabilitation on health-related outcomes and whether rehabilitation should be implemented more widely across the NHS or withdrawn if there is no evidence of improved outcomes for patients.

1.2 Existing knowledge

National Institute for Health and Care Excellence (NICE) guidance currently advises that the recovery pathway following critical illness should include regular assessment of physical and non-physical morbidity, goal setting, multi-professional rehabilitation input according to individualised needs, and transition of information between care delivery stages (15). However, this practice has either been applied poorly or not at all following hospital discharge, and rehabilitation services post-critical illness in the UK are ad hoc, geographically inconsistent, and variable in terms of structure, content, and format of delivery (16). A survey of 242 UK hospitals conducted in 2020 found that few responding hospitals offered a post-discharge physical rehabilitation programme (31/176, 18%) (17).

Exercise programmes can aid physical recovery in people with chronic obstructive pulmonary disease, chronic fatigue, and congestive heart failure (18-20). Our Cochrane systematic review found that evidence for the effectiveness of post-hospital discharge rehabilitation interventions for survivors of critical illness was inconclusive (21, 22). Nonetheless, findings from qualitative studies suggest that individual's experience of participating in rehabilitation programmes is markedly positive across domains of health, wellbeing, and perceived rate and quality of recovery (23). This suggests that the primary indicator of clinical effectiveness for these complex, multifactorial interventions may lie not only in objective markers of physical symptoms, but in measures reflecting broader aspects of quality of life. Individual's needs after critical illness are multifaceted (24) and we found that people

specifically re-enforced the need for multicomponent rehabilitation as well as a more individualised approach (25).

1.3 Need for a trial

There is evidence to support the rehabilitation of critically ill patients within ICU, but a paucity of literature to support rehabilitation following discharge from ICU and hospital (26). Of the four Cochrane systematic reviews that explore rehabilitation after critical illness, there are no trials that address remote rehabilitation or technology enhanced care for post-hospital discharge rehabilitation in survivors of critical illness. No such trials are currently registered. Technology-enabled care has been shown to be effective and accessible for delivery of rehabilitation in other illnesses and settings e.g. cardiac rehabilitation, balance rehabilitation in older people, chronic obstructive pulmonary disease (27-35) but this needs to be tested in people after critical illness before widespread implementation in the NHS. We also need feasible methods and alternative approaches to provide rehabilitation to patients during ongoing pandemic restrictions. Our proposed intervention includes strategies to improve recovery, collectively delivered in an efficient format for ease of user-accessibility in a modern health service. The active intervention will be delivered remotely and accommodates accessibility issues, including ethnic diversity as well as being acceptable for those from more deprived socioeconomic areas. Therefore, it provides a real opportunity to scale a rehabilitation service to be available to everyone in the UK who could benefit, irrespective of geographic location, ethnicity or income.

In summary, this trial provides an opportunity to deliver a definitive trial for the pragmatic evaluation of a remote multicomponent rehabilitation programme targeting survivors of critical illness following discharge from the ICU in whom post-hospital morbidity is substantial. This trial will be the first to systematically test a technology-driven remote approach to evaluate the clinical and cost-effectiveness of a rehabilitation intervention in patients recovering from critical illness after ICU care.

1.4 Hypothesis

Hypothesis: For people following a hospital admission that included admission to an ICU for a critical illness, a six-week remote multicomponent rehabilitation intervention improves health-related quality of life, physical function, fatigue, mood, and other health-related outcomes after eight weeks, compared to best practice standard care.

1.5 Aims and objectives

1.5.1 Aim

The overall aim of this trial is to investigate, in survivors of critical illness following discharge from hospital after an Intensive Care Unit (ICU) admission, the effects of a six-week remote multicomponent rehabilitation intervention compared to standard care on health-related quality of life at eight weeks post-randomisation.

1.5.2 Objectives

Trial objectives are:

- a) To investigate the effects of a six-week remote multicomponent rehabilitation intervention compared to standard care on physical function, illness perceptions, fatigue, anxiety, depression, and adverse events at eight weeks post-randomisation.
- b) To investigate longer term effects of a six-week remote multicomponent rehabilitation programme compared to standard care on health-related quality of life, physical function, illness perceptions, fatigue, anxiety, and depression at six months post-randomisation.
- c) To determine explanatory factors influencing outcomes via an embedded process evaluation.
- d) To evaluate the cost-effectiveness of the multicomponent rehabilitation intervention compared to standard care over six months follow-up.

2. TRIAL DESIGN

2.1 Trial Summary

Trial Design: Pragmatic, randomised (allocation ratio 1: 1.17), controlled, assessor blind, multi-centre trial with internal pilot and embedded process evaluation.

Setting: At least 30 NHS hospitals across UK.

Population: Adults (≥18years) within 12 weeks of discharge from hospital that included an ICU admission for critical illness, requiring mechanical ventilation ≥48hours.

Sample size: 428 participants (control n= 197; intervention: n=231).

Intervention: Six week multicomponent, rehabilitation intervention, delivered remotely by a core intervention team. In brief, the intervention includes four components: weekly symptom management; targeted exercise; psychological support and information/peer support.

Control: Standard Care, **not** involving structured rehabilitation.

Outcomes: primary - health-related QoL at eight weeks post-randomisation; secondary outcomes: health-related QoL (at six months), physical function, fatigue, anxiety and depression, healthcare resource use at eight weeks and six months post-randomisation and intervention acceptability at 8 weeks

Internal pilot: An internal pilot will test recruitment processes and intervention-related procedures, with planned seamless transition to the main trial, after review and approval of stop-go criteria. The internal pilot phase will include qualitative interviews with participants taking part in the rehabilitation intervention, intervention team members and trial staff

2.2 Outcome measures

2.2.1 Justification for primary outcome

The trial primary outcome is **health-related quality of life**, measured using the EQ-5D-5L at **eight weeks** post-randomisation. Health-related QoL is multidimensional, encompassing components of physical, psychological, emotional, and social wellbeing. The EQ-5D-5L is the recommended measure for assessing quality of life in core outcome sets for longer-term outcomes following respiratory failure and physical rehabilitation in critical illness (36, 37). Systematic reviews confirm the EQ-5D-5L to be similarly robust compared with other longer measures, such as the SF-36 (38, 39). The scale measures mobility, self-care, usual activities, pain/discomfort, and anxiety/depression from no problems to severe problems. These domains and the visual analogue scale (VAS 0-100mm) capturing health utility are widely used for health economic evaluation. The scale was responsive to change in a study assessing multicomponent rehabilitation in post-critical illness patients (40), and has been validated for telephone completion. Importantly, our PPI group endorsed quality of life as an important outcome to reflect recovery after critical illness. Our PPI partners also confirmed assessment time-points were appropriate and feasible from a patient perspective. Follow-up time-points of eight weeks and six months mirror previous rehabilitation research, including remotely delivered interventions, with six months being of adequate duration to capture changes over time (41).

2.2.2 Justification for secondary outcomes

People typically report a range of symptoms and disability with varying levels of severity and magnitude after critical illness (2-11, 23-25). It is important to capture how rehabilitation may impact upon multiple symptoms, using measures feasible for remote data collection, including postal, online, and/or telephone follow-up (42,43), 38-40, 44). Our trial outcomes are similar to outcomes included in other studies investigating remote pulmonary rehabilitation and remote exercise testing (42, 43). Secondary outcomes in iRehab include valid and reliable tools to measure physical strength (8,45,46), fatigue and emotional wellbeing, including symptoms of anxiety and low mood (46,47). Health and social care data will be collected for health economic analyses.

Efficacy

Primary outcome

Health-related quality of life – EQ-5D-5L (38-40, 44) measured at eight weeks post-randomisation.

Secondary outcomes

Secondary outcomes will be measured at eight weeks and six months.

- Physical Function – 30 second sit to stand test (45)
- Illness Perception – Brief Illness Perception Questionnaire (46)
- Fatigue – Functional Assessment of Chronic Illness Therapy-Fatigue (FACIT-F) scale (8)
- Anxiety and Depression – Hospital Anxiety and Depression Scale (HADS) (47)
- Intervention acceptability data will be collected as recommended the MRC guidance for evaluating complex interventions (75)

Safety

- We will collect data on serious adverse events as described in Section 4.

Others

- Healthcare and social care utilisation questionnaire for health economic analyses

Timing of outcome assessments

All measures will be collected at baseline (pre-randomisation), **eight weeks** and **six months** post-randomisation. The eight-week follow-up is one to two weeks after planned completion of the rehabilitation programme.

Follow-up outcome assessments

Follow-up questionnaires will be completed **remotely online or by telephone** (or postal as exception) at eight weeks and six months, coordinated by WCTU trial office. An email and/or text message will be sent to participants asking them to click on a link which will take them to the online questionnaire portal or they will receive a call to arrange a time to complete the questionnaire verbally via phone. The 30-second sit-to-stand test will be captured by a iRehab researcher using remote consultation and will be conducted as soon as possible aiming to complete it within one week from the completion of the patient reported outcomes. Reminders will be sent to non-responders after two weeks following WCTU processes. The minimum core data set will include the EQ-5D-5L at eight weeks and six months.

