2.7 Trial interventions

2.7.1 Comparator - Standard Care

Standard NHS care, without active rehabilitation, will be the trial comparator. Hospitals offering active structured physical rehabilitation as part of usual care, will not be eligible to participate. For participants randomised to standard care, no further intervention will be offered after completion of baseline assessment and randomisation, other than usual NHS care. Data on healthcare resource use will be collected from all participants over the six-month trial period. We will record what standard care has been received at an individual level for all participants across the trial period, and as well as resource use across the trial period.

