3. METHODS AND ASSESSMENTS

3.1 Schedule of delivery of intervention and data collection

An overview of schedule of trial assessments is given in Table 3.

Table 3 – Schedule of delivery of data collection

	Pre-randomisation		Post-randomisation			
	Screening	Baseline	Intervention	Follow-up		
Weeks ± No. Days	Weeks 0-12		Weeks 1-6	Week 8	8-26 weeks	Week 26
Check eligibility	✓	✓				
Consent participant		✓				
Clinical data collection (by site)						
APACHE II score		✓				
Medical history		✓				
Co-morbidities		✓				
Pre-ICU admission functional status		✓				
Duration ventilation		✓				
Length of ICU stay		✓				
Length hospital stay		✓				
Participant data collection						
EQ-5D-5L		✓		✓		✓
30sec Sit-to-Stand		✓		✓		✓
BIPQ		✓		✓		✓
FACT-F		✓		✓		✓
HADS		✓		✓		✓
Health and social care use				✓		✓
TFAQ				✓		
Randomisation		R*				
Intervention delivery			✓			
Process evaluation						

	Pre-randomisation		Post-randomisation			
	Screening	Baseline	Intervention	Follow-up		
Weeks ± No. Days	Weeks 0-12		Weeks 1-6	Week 8	8-26 weeks	Week 26
					✓	
Participant self-report/Site data collection						
AEs		✓	✓	✓		✓
SAEs		✓	✓	✓		✓

*Randomisation after consent and participant baseline data collection. Refer to outcome section for questionnaire measures.

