7.8 Health Economic Evaluation

A prospective within-trial economic evaluation, adhering to NICE Reference Case recommendations (67) will compare intervention with standard care. Healthcare resource use data will include in-patient and community care health service contacts during the six-month follow-up period, collected via trial CRFs and costed using the most recently available published reference costs. Generic HRQoL will be assessed at baseline, eight weeks and six months using the EQ-5D-5L, with responses converted to health status scores using the NICE-recommended UK value set and sensitivity analyses conducted using alternative tariffs if this is likely to be useful for decision-making (74). Patient-level QALY estimates will be calculated using the trapezoidal rule. Analyses will

explore and manage data missingness in line with the approach described in section 7.6. Every effort will be made to minimize missingness, but if appropriate, a suitable method such as multiple imputation will be used to account for missingness. Bootstrapped bivariate regression will estimate and visualize incremental cost-effectiveness ratios, acceptability curves and net monetary benefit. If findings are non-convergent at six months, we will explore the sensitivity of cost-effectiveness to extrapolation of costs and benefits beyond the trial time horizon, via a suitable decision model or parametric survival analysis model. Value of information analysis will be conducted to explore the sensitivity of health economic recommendations to additional research. Sensitivity analyses will also explore the impact of broadening the decision perspective beyond the NICE reference case to include indirect costs such as the impact on productivity. Additional secondary cost-effectiveness analyses will also explore the unit cost of any achieved reductions in fatigue or anxiety/depression resulting from the intervention.

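### The Trial Summary and section 2.2.2 promise a pre-randomisation measure of health and social care use, but Table 3 schedules it only at weeks 8 and 26; the cost comparison stays valid but loses some precision.

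*Protocol*

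**What the plan says.** Two places put the resource-use measure before randomisation:

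- Protocol section 2.2.2 lists, under its other measures, the "Healthcare and social care utilisation questionnaire for health economic analyses". The timing paragraph just below says "All measures will be collected at baseline (pre-randomisation"), at eight weeks and at six months. It makes no exception.
- The Trial Summary heads its outcome list "Measured pre-randomisation, eight weeks, six months post-randomisation". Health and social care utilisation is one of the items in that list.

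Table 3 in section 3.1 does not. Its row "Health and social care use" has ticks at weeks 8 and 26 and none at baseline.

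Three other sections bear on the question:

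- Section 2.1 gives "healthcare resource use at eight weeks and six months post-randomisation and intervention acceptability at 8 weeks".
- Section 2.7.1 says "Data on healthcare resource use will be collected from all participants over the six-month trial period".
- Section 7.8 says "Healthcare resource use data will include in-patient and community care health service contacts during the six-month follow-up period", and plans the analysis thus: "Bootstrapped bivariate regression will estimate and visualize incremental cost-effectiveness ratios, acceptability curves and net monetary benefit". It does not mention adjustment for baseline cost.

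**The concern.** The assessment schedule belongs in the protocol, and here the protocol gives two answers. If the database follows Table 3, a form promised in two places is never issued, and service use before randomisation cannot be collected well afterwards.

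This bears on a stated aim. Cost-effectiveness is in the full title and is objective (d). Participants may consent at any time up to 12 weeks after discharge, and section 1.1 reports that one in four survivors has an unplanned readmission within 90 days of discharge. Someone who consents at the 12-week limit has already passed 84 of those 90 days; someone who consents at one week has passed 7. Service use before randomisation will therefore differ widely between participants. The minimisation in section 2.6 uses only site and duration of ventilation, so the design balances neither prior use nor time since discharge.

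Baseline use would also help to impute missing costs, which section 7.8 allows for. Section 7.1 plans for 30% loss to follow-up, which is 0.30 × 428 ≈ 128 participants.

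**Working it through.** **Step 1. Is the blank in Table 3 real?** The EQ-5D-5L, sit-to-stand, BIPQ, fatigue and HADS rows each have three ticks: baseline, week 8 and week 26. The resource-use row has two, set in the week 8 and week 26 columns. The TFAQ row has one, at week 8. The pattern is consistent across rows, so the blank does not look like a text-extraction fault.

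**Step 2. Do other sections settle the matter?**

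| Place | Timing of resource use | Settles it? |
|---|---|---|
| Trial Summary | baseline, 8 weeks, 6 months | no; the same heading also covers the TFAQ |
| Section 2.2.2 | baseline, 8 weeks, 6 months | no; it also sweeps in intervention acceptability |
| Section 2.1 | 8 weeks, 6 months | no; fatigue, anxiety and depression get the same timing, yet Table 3 ticks them at baseline |
| Table 3 | weeks 8 and 26 | conflicts with the first two |
| Sections 2.7.1 and 7.8 | six-month period | no; they define the costing window and do not rule out a baseline covariate |

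**Step 3. What does the absence cost?** The protocol gives no figure to reproduce. The usual approximation for adjusting on one baseline covariate is:

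- share of cost variance removed = r²
- narrowing of the confidence interval = 1 − √(1 − r²)

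Here r is the correlation between baseline and follow-up cost. The protocol does not give r, so the range below is an assumption.

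| r (assumed) | Variance removed | Narrowing |
|---|---|---|
| 0.1 | 1% | 1 − √0.99 = 0.5% |
| 0.2 | 4% | 1 − √0.96 = 2.0% |
| 0.3 | 9% | 1 − √0.91 = 4.6% |
| 0.5 | 25% | 1 − √0.75 = 13.4% |

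**Step 4. Allow for what is already collected.** Table 3 and section 2.5.4 provide baseline EQ-5D-5L, co-morbidities, medical history, APACHE II, pre-ICU function, ventilation duration, and ICU and hospital stay. If these enter the cost equation, the relevant r is the partial correlation given them, which will normally be smaller. The figures in step 3 are therefore best read as upper values for each assumed r.

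**The case against.** The strongest reply is that the intent is clear and only the wording is loose. Table 3, section 2.1, section 2.7.1 and section 7.8 all describe resource use after randomisation. The section 2.2.2 sentence cannot be literally true, because it would require participants to rate the acceptability of an intervention before being allocated to it. On this view the repair is to correct that sentence, not to add a form. Part of this stands: the sentence is too broad, and dropping the baseline promise would be a legitimate resolution. But as step 2 shows, the other sections do not exclude a baseline measure, so the sponsor still has to say which applies.

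Three stronger readings are tempting and are not supported:

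- A reader might infer that the cost comparison is biased or cannot be carried out. It is not. Costs accrue after randomisation, so the randomised difference is unbiased in expectation without a baseline value. Section 7.8 states no baseline-cost adjustment that would be left without its input.
- A reader might infer that nothing about prior service use is recorded. That goes too far. The index ICU and hospital stay (section 2.5.4), baseline medication (section 2.10.2) and site-reported readmissions (section 5.5) give partial information. None is stated to cover community or social care contacts between discharge and randomisation.
- A reader might infer that section 2.2.2 would capture the whole period before randomisation. It states no recall period, so its coverage is unknown.

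Nor does the protocol say that Table 3 governs the database. Section 6.2 leaves the specifications to be agreed between the programmer and trial staff. The loss is therefore conditional on Table 3 being followed.

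**Conclusion.** The inconsistency is real: the Trial Summary and section 2.2.2 include a baseline measure of health and social care use, and Table 3 does not. The primary outcome and the validity of the six-month cost comparison are unaffected.

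If Table 3 is followed, the loss is modest: some precision, protection against chance imbalance in prior service use, and an imputation predictor. The forgone narrowing of the incremental-cost interval is about 0.5% to 13%. This rests on an assumed correlation of 0.1 to 0.5 and on no credit for covariates already collected; with that credit it is less. Adding the baseline form is a cheap improvement to a stated objective, not a repair of an invalid analysis. It is worth deciding early because the data are hard to recover later.

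**What to change.** Reconcile the Trial Summary, section 2.2.2 and Table 3. The preferred route is:

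- Tick health and social care use at baseline in Table 3.
- State the recall period, for example since hospital discharge, and record the discharge date so that use can be expressed over a known length of time. Rates will be noisy for people discharged only days earlier, which is a further reason to expect a modest gain.
- Include baseline use in the cost equation of the bivariate regression and in any imputation model for costs under section 7.8.

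The cost is one existing questionnaire, with its recall wording adapted, in the baseline pack, one added covariate, and a few minutes of participant time.

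If the sponsor decides against a baseline form, the Trial Summary and section 2.2.2 should exempt resource use from the baseline statement. In either case both should exempt the TFAQ, which Table 3 collects at week 8 only.
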